5.2.3. Analyses for Categorical Endpoints

Frequency and percentage for each category of the variable will be provided as a descriptive summary for each visit. For example, the frequency and percentage of the stage 1 to 5 for tanner stage will be presented at Baseline and Month 12.

5.2.4. Analyses for Time-to-Event Endpoints

Not applicable.

5.3. Methods to Manage Missing Data

The missing data for the primary and secondary efficacy endpoints analyzed by the Wilcoxon signed rank test will be imputed using last observation carried forward (LOCF) method in FAS, ie, the measurement obtained at the early termination visit will be used to impute the Month 12 data.

For imaging-based endpoints, the spleen volume and liver volume measured by the MRI at the early termination visit will be taken as the Month 12 measurement, if the Month 12 visit is missing. If there is no post-baseline MRI measurement, the percentage change from baseline to Month 12 in organ volumes by ultrasound can be used to impute the missing percentage change from baseline in organ volumes by MRI per clinical judgment. The percentage change from baseline needs to be derived within the same imaging test, ie, based on post-baseline organ volume measured by ultrasound and baseline organ volume measured by ultrasound. If there is no post-baseline imaging measurement, the baseline observation carried forward (BOCF) will be applied for missing data, ie, the baseline volume measured by MRI will be used to impute Month 12 MRI data.

Missing safety data will be handled according to the Pfizer Clinical Data Interchange Standards Consortium (CDISC) safety rulebook and data standard rules for imputation, including missing dates (when the date is required for a calculation) and missing severity of adverse events.

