9. STUDY PROCEDURES AND FLOW CHART

9.1 Study Flow Chart

Table 1: Study Flow Chart

Activity	Visit 0 Screening	Visit 1 Baseline	Visits 2-5	Visit 6	Visit 7 Month 3	Visits 8-13	Visit 14 Month 6	Visits 15-19	Visit 20 Month 9	Visits 21-26	Visit 27 Month 12
	Day -50 ±10	Day 1	Weeks 2, 4, 6, 8, (±3 days)	Week 10 (±3 days)	Week 12 (±7 days)	Weeks 14, 16, 18, 20, 22, 24 (±3 days)	Week 26 (±7 days)	Weeks 28, 30, 32, 34, 36 (±3 days)	Week 38 (±7 days)	Weeks 40, 42, 44, 46, 48, 50 (±3 days)	Week 52 ^d (±7 days)
Sign informed consent	X										
Review inclusion/exclusion criteria	X										
Demographics	X										
Medical history	X										
Current/concomitant medications	X	X	X	X	X	X	X	X	X	X	
Weight/height	X	X			X		X		X		X
Physical examination	X	X			X		X		X		X
Neurologic assessment	X						X				X
Hematology	X	X			X		X		X		X
Biochemistry ^{f,g}	X	X			X		X		X		X
Urinalysis	X	X			X		X		X		X
Serology (HIV, HBsAg, HCV)	X										
TSH, free T4, transferrin, B ₁₂ and folic acid	X										
Beta HCG (post-menarcheal girls)	X										
Vital signs ^h	X	X	X	X	X	X	X	X	X	X	
Anti-taliglucerase alfa antibodies		X				X					X
Organ volumes (MRI)	X										X
Ultrasound (liver and spleen)	X						X				X
Echocardiography	X										
Tanner Stage		X									X
X-ray of left hand and wrist		X									X
DEXA		X									X
mSST	X						X				X
Molecular analysis ^e	X										
Lyso-Gb1 biomarker		X			X		X		X		X
Chitotriosidase		X			X		X		X		X
IV infusion of taliglucerase alfa		X ^a	X ^b	X	X ^c	X	X ^c	X	X ^c	X	X ^c
Observe subject clinically		X	X		X		X		X		X
Evaluate injection site		X	X		X		X		X		X
Adverse events	X	X	X	X	X	X	X	X	X	X	X

DEXA = dual-emission X-ray absorptiometry; HBsAg = hepatitis B surface antigen; HCG = human chorionic gonadotropin; HCV = hepatitis C virus; HIV = human immunodeficiency virus, IV = intravenous; MRI = magnetic resonance imaging; T4 = thyroxine; TSH = thyroid stimulating hormone

- ^a A follow-up telephone call with the subject and/or parent or guardian will be held the day after the infusion.
- ^b Subjects who tolerate the infusions will be eligible for transfer to home or infusion center treatment after this visit at the discretion of the Investigator and Medical Monitor.
- ^c Taliglucerase alfa infusion must be done at the subject's selected medical center.
- ^d All Month 12 (Week 52) procedures/assessments are to be done for any subject who withdraws or is discontinued from the study before completion.

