9.2.12 Early Termination Visit

If the subject withdraws or is discontinued from the study before completion, the reason for discontinuation must be documented in the subject's CRF. Whenever a subject is discontinued, the procedures/assessments listed in [Section 9.2.11](#) should be conducted, unless advised otherwise by the Medical Monitor.

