3.1. Primary Endpoint

The primary efficacy evaluation will be the percent change in spleen volume (expressed in MN) measured by MRI from baseline to Month 12.

Spleen volume will be measured at the Screening and Month 12 according to the Schedule of Activities in Section 9 of the protocol, measured by MRI by site according to the Appendix 4 of the protocol. The spleen volume (cm^3) will be used for the sponsor to calculate the spleen volume by multiples of normal (MN) data applying the formula below:

$$\text{Spleen Volume by MN} = \frac{\text{Spleen Volume}}{2\text{cm}^3 / \text{kg} * \text{body weight}}$$

When body weight (kg) is not available at a visit, the body weight measured in the previous visit will be used to estimate the participant's expected normal volume at the visit.

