6.1.2. Sensitivity/Supplementary Analyses

Sensitivity analyses

- To assess the impact of early discontinuation, the same Wilcoxon signed rank test will be repeated in the PP set ([Section 4](#)) among those who have the primary efficacy data collected by MRI at Month 12 and Baseline.
- Descriptive summary for absolute value, change from baseline and percent change from baseline in spleen volume and spleen volume MN measured by MRI at each visit will be repeated in the PP set.

Supplementary analysis

- In addition to the main analysis on the primary estimand, the supportive analysis on the alternative estimand of the binary responder rate based on spleen volume MN reduction measured by MRI will be provided in FAS. This includes the frequency and percentage of the responders, as well as the 95% confidence interval (CI) for the responder rate using exact Clopper-Pearson method. The supportive evidence can be obtained, if the lower bound of the 95% CI excludes the responder rate of 50%.

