9. APPENDICES

Appendix 1. Summary of Efficacy Analyses

Endpoint	Analysis Type	Population	Data Inclusion and Rules for Handling Intercurrent Events and Missing Data	Analysis Model
Percent change from baseline to Month 12 in spleen volume MN measured by MRI	Summary	Evaluable (FAS), PP	observed data at each visit	N/A
	Main analysis	Evaluable (FAS)	Month 12 or data from early termination assessment and baseline	Wilcoxon signed rank test (exact p-value), median %change
	Sensitivity analysis	PP	completed both Month 12 and baseline without missing data imputation	Wilcoxon signed rank test (exact p-value), median %change
Responder rate in spleen volume reduction measured by MRI	Supplementary analysis	Evaluable (FAS)	Month 12 or data from early termination assessment and baseline	Clopper-Pearson CI
Percent change from baseline to Month 12 in liver volume MN measured by MRI	Summary	Evaluable (FAS)	observed data at each visit	N/A
	Main analysis	Evaluable (FAS)	Month 12 or data from early termination assessment and baseline	Wilcoxon signed rank test (exact p-value), median %change
Percent change from baseline in hemoglobin	Summary	Evaluable (FAS)	observed data at each visit (baseline, Month 3, 6, 9, 12)	N/A
	Main analysis	Evaluable (FAS)	Month 12 or data from early termination assessment and baseline	Wilcoxon signed rank test (exact p-value), median %change
Percent change from baseline in platelet	Summary	Evaluable (FAS)	observed data at each visit (baseline, Month 3, 6, 9, 12)	N/A
	Main analysis	Evaluable (FAS)	Month 12 or data from early termination assessment and baseline	Wilcoxon signed rank test (exact p-value), median %change
Percent change from baseline in Lyso-Gb1	Summary	Evaluable (FAS)	observed data at each visit (baseline, Month 3, 6, 9, 12)	N/A
	Main analysis	Evaluable (FAS)	Month 12 or data from early termination assessment and baseline	Wilcoxon signed rank test (exact p-value), median %change

Endpoint	Analysis Type	Population	Data Inclusion and Rules for Handling Intercurrent Events and Missing Data	Analysis Model
Percent change from baseline in chitotriosidase	Summary	Evaluable (FAS)	observed data at each visit (baseline, Month 3, 6, 9, 12)	N/A
	Main analysis	Evaluable (FAS)	Month 12 or data from early termination assessment and baseline	Wilcoxon signed rank test (exact p-value), median %change
Change from baseline in height SDS	Summary	Evaluable (FAS)	observed data at each visit	N/A

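### SAP 5.3 carries forward the baseline MRI volume although the endpoint is weight-adjusted MN, and leaves ultrasound substitution to judgment that may be made with the result in view

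*SAP*

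**What the plan says.** SAP 5.3 gives an ordered scheme for a missing Month 12 organ volume, and SAP 6.1.1 applies it to the primary analysis in the FAS.

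- An early-termination MRI stands in for Month 12.
- With no post-baseline MRI, the ultrasound percent change from baseline to Month 12 "can be used to impute the missing percentage change from baseline in organ volumes by MRI per clinical judgment". It must be derived within ultrasound.
- "If there is no post-baseline imaging measurement, the baseline observation carried forward (BOCF) will be applied for missing data". The SAP spells this out: "the baseline volume measured by MRI will be used to impute Month 12 MRI data".

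SAP 3.1 defines spleen MN as volume / (2 cm³/kg × body weight), calculated by the sponsor. If weight is missing at a visit, "the body weight measured in the previous visit will be used to estimate" the expected normal volume. SAP 3.4 sets baseline for spleen volume at Screening.

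The decision rule (SAP 5.1 and 6.1.1) is an exact two-sided Wilcoxon signed rank test of the percent change in MN against −20%, run after adding 20 points to each value. As a sensitivity analysis without imputation, "the same Wilcoxon signed rank test will be repeated in the PP set" (SAP 6.1.2).

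The Protocol limits how often imputation is needed. Month 12 "procedures/assessments are to be done for any subject who withdraws or is discontinued from the study before completion" (Protocol 9.1, note d), although Protocol 9.2.12 adds "unless advised otherwise by the Medical Monitor".

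**The concern.** The quantity carried forward and the quantity tested are on different scales. No section says which weight accompanies the carried volume, that MN is carried, or that the change is 0%. Two programmers could therefore derive different values for the same unscanned participant. Under the literal derivation, the imputed value reflects the participant's weight and not the spleen.

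The ultrasound step raises two issues. Its wording also refers to organ volumes, so it is unclear whether the percent change is taken in cm³ or in MN. And whether to use it is left open: no basis for the judgment is given, nothing requires it before the percent change is known, and if an available ultrasound is declined the BOCF trigger (no post-baseline imaging) is not met, so no stated rule applies. In an uncontrolled trial that plans on as few as 9 completers, one imputed value can matter to the primary test.

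**Working it through.** **1. Is volume the literal reading?** Protocol Appendix 14.4.3 lists the MRI output as spleen and liver volume in cm³. SAP 6.1.1 summarises spleen volume and spleen volume MN as separate variables, and says that imputed values enter the calculation of percent change. So volume is imputed first and MN derived afterwards, which requires a weight.

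**2. Imputed MN change under that reading.** With volume V held fixed:

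(V/(2·W1)) / (V/(2·W0)) − 1 = W0/W1 − 1.

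The documents give no weight changes, so these are assumptions:

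| Weight change | Imputed MN change | After the +20 shift |
|---|---|---|
| −5% | 1/0.95 − 1 = +5.3% | 25.3 |
| −2% | 1/0.98 − 1 = +2.0% | 22.0 |
| 0 | 0% | 20.0 |
| +2% | 1/1.02 − 1 = −2.0% | 18.0 |
| +5% | 1/1.05 − 1 = −4.8% | 15.2 |

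If no later weight exists, the previous-visit rule returns the earlier weight and the change is about 0%.

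**3. The same ambiguity in the ultrasound step.** A cm³ change of v corresponds to an MN change of (1 + v)·W0/W1 − 1. With an assumed v = −18% and a 5% gain, 0.82/1.05 − 1 = −21.9%. That is beyond the −20% threshold in MN but short of it in cm³.

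**4. The plan's own figure.** Protocol 10.1 uses 9 evaluable subjects, responder rate 0.91 against 0.5. Rejecting at 8 or more of 9, power is 9 × 0.91⁸ × 0.09 + 0.91⁹ = 0.809, and two-sided alpha is 2 × 10/512 = 0.039. Both match the stated 80.9% and 0.04. The 0.91 anchors step 5.

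**5. Effect on the primary test, given one BOCF participant.** Completers' changes are drawn as normal with P(change < −20%) = 0.91, so mean = −20 − 1.341 × SD. The SD is assumed: 10 (mean −33.4%) or 15 (mean −40.1%). One imputed value is added, and success is exact p < 0.05 in the direction of reduction (200,000 trials).

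| Completers | SD | 0% imputed | 2% gain | 5% gain | 2% loss |
|---|---|---|---|---|---|
| 9 | 10 | 0.430 | 0.535 | 0.658 | 0.317 |
| 9 | 15 | 0.720 | 0.754 | 0.795 | 0.676 |
| 12 | 10 | 0.867 | 0.887 | 0.913 | 0.845 |
| 12 | 15 | 0.927 | 0.936 | 0.947 | 0.917 |
| 14 | 10 | 0.951 | 0.958 | 0.968 | 0.944 |
| 14 | 15 | 0.974 | 0.977 | 0.981 | 0.970 |

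At 5% gain, the difference from imputing 0% is +22.8 and +7.5 points with 9 completers, +4.6 and +2.0 with 12, and +1.7 and +0.7 with 14.

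**6. When a result would flip.** With 9 completers all below −20% and one imputed value above it, exact p is 0.037, 0.049, 0.064 or 0.084 when the imputed value has rank 7, 8, 9 or 10 in absolute size. Weight changes the conclusion only by moving that value between ranks 8 and 9. For assumed completer changes of −28, −31, −34, −36, −37, −38, −39, −42 and −46%, p is 0.049 at 0%, 0.037 at 2% gain and 0.014 at 5% gain. A gain causes no flip, but a 2% loss gives 0.064.

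**The case against.** The strongest reply is that SAP 5.3 names the method baseline observation carried forward, for which no change is the natural result, and uses the word volume loosely throughout. On that view this is a matter of wording. The reply has some force, but the SAP separates volume from MN elsewhere, so the literal reading is open to a programmer and one sentence would close it. The looseness also extends the ambiguity to the ultrasound step.

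The second reply is rarity, and it stands. BOCF needs no Month 12 MRI, no early-termination MRI and no post-baseline ultrasound. Because ultrasound is also scheduled at Month 6, the last scheduled weight would usually be from Day 1 or Month 3, and the weight change small. The largest figures need 9 completers, SD 10 and one BOCF case together. SD 15 fits the pediatric 60 units/kg medians in Protocol Appendix 14.1 better (18.4 to 11.0 MN, 11.0/18.4 − 1 = −40%). Protocol 4.3.3 reports smaller changes in Type 3 patients, so SD 10 is not excluded.

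Three stronger readings are tempting but not supported:

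- **The rule favours the drug.** Its direction follows weight, which can go either way, and the documents give no weight data.
- **Any ultrasound at any time may be substituted.** The step refers to change to Month 12, and SAP Appendix 2.1 sets a 42-day imaging window on either side. What is missing is when the judgment is made.
- **Appendix 1 contradicts SAP 5.3.** Its main-analysis row reads "Month 12 or data from early termination assessment and baseline", but it is a summary table and SAP 6.1.1 refers to Section 5.3. That omission, and the unclear position of a participant with only a Month 6 ultrasound, are missing detail.

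**Conclusion.** The gap in the text is real and sits in the decision analysis, but its priority is low. As written, BOCF can give an unscanned participant a non-zero MN change that comes only from weight. The ultrasound step leaves both the scale and the decision open, with no fallback if a scan is declined.

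The simulated sizes are conditional on one BOCF participant, a normal distribution, an assumed SD of 10 to 15 and an assumed weight change. They are not estimates of the expected effect on the trial, because the documents do not allow the frequency of either branch to be estimated. The per-protocol analysis would reveal a dependence on imputation but does not decide efficacy.

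**What to change.** 1. State in SAP 5.3 that BOCF carries the baseline MN, so that the imputed percent change in MN is 0%.
2. State that the ultrasound percent change is computed in MN. The decision to use or decline it should rest on documented evaluability of the scans, made before the percent change is seen and before database lock, with BOCF applying if it is declined.

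The same edit can state a rule for a participant with only a Month 6 ultrasound and repeat the order in Appendix 1.

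The cost is a few sentences and minor programming. The FAS result may become slightly less favourable after weight gain and more favourable after weight loss. SAP 3.3.5 derives ultrasound volume as a plain product of three dimensions, so some clinicians may want wider discretion. Evaluability still lets them decline a poor scan, but not because of its result. For liver MN, which is tested against 0, a 0% change is dropped under SAP 5.2.2. The SAP should say that such a participant does not contribute to that test.

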6. ANALYSES AND SUMMARIES

6.1. Primary Endpoint

6.1.1. Main Analysis

- Estimand strategy: Treatment policy strategy for percent change from baseline to Month 12 in spleen volume MN measured by MRI.
- Analysis set: FAS (defined in [Section 4](#)). All participants assigned to study drug and received at least 1 complete dose of taliglucerase alfa (or partial dose if adverse events prevent completing infusion dose) will be included.
- Analysis methodology: Percent change from baseline to Month 12 will be analyzed using Wilcoxon signed rank test detailed in [Section 5.2.2](#). In order to judge whether this primary efficacy endpoint meets the 20% reduction from baseline, a 20% shift will be added on the percent change from baseline for each participant in the analysis set before the procedure of Proc Univariate ([Appendix 4](#)).

- Intercurrent events and missing data: Data after study drug discontinuation will be included. Missing values will be imputed using LOCF and other methods specified in [Section 5.3](#) and be included in calculating percent change from baseline.
- Summary of statistical comparison: The 2-sided p-value from the exact inference for Wilcoxon signed rank statistics for comparing Month 12 to baseline value, as well as the median percent change from baseline, will be presented and used to judge whether efficacious criteria is met. The n, minimum and maximum for the observed percent change from baseline will be presented together as well.
- Descriptive summary including n, mean, SD, median, minimum, and maximum for absolute value, change from baseline and percent change from baseline in spleen volume and spleen volume MN measured by MRI at each visit will be presented.

6.1.2. Sensitivity/Supplementary Analyses

Sensitivity analyses

- To assess the impact of early discontinuation, the same Wilcoxon signed rank test will be repeated in the PP set ([Section 4](#)) among those who have the primary efficacy data collected by MRI at Month 12 and Baseline.
- Descriptive summary for absolute value, change from baseline and percent change from baseline in spleen volume and spleen volume MN measured by MRI at each visit will be repeated in the PP set.

Supplementary analysis

- In addition to the main analysis on the primary estimand, the supportive analysis on the alternative estimand of the binary responder rate based on spleen volume MN reduction measured by MRI will be provided in FAS. This includes the frequency and percentage of the responders, as well as the 95% confidence interval (CI) for the responder rate using exact Clopper-Pearson method. The supportive evidence can be obtained, if the lower bound of the 95% CI excludes the responder rate of 50%.

6.2. Key Secondary Endpoints

6.2.1. Main Analysis

- Estimand strategy: Treatment policy strategy for percent change from baseline to Month 12 in liver volume MN measured by MRI, hemoglobin, platelet and Lyso-Gb1 (lyso-glucosylsphingosine), chitotriosidase.
- Analysis set: FAS (defined in [Section 4](#)). All participants assigned to study drug and received at least 1 complete dose of taliglucerase alfa (or partial dose if adverse events prevent completing infusion dose) will be included.

- Analysis methodology: Percent change from baseline to Month 12 will be analyzed using Wilcoxon signed rank test detailed in [Section 5.2.2](#).
- Intercurrent events and missing data: Data after study drug discontinuation will be included; Missing values will be imputed using LOCF, and other methods specified in [Section 5.3](#), and included in calculating percent change from baseline.
- Summary of statistical comparison: The 2-sided p-value from the exact inference for Wilcoxon signed rank statistics for comparing Month 12 to baseline value, as well as median percent change from baseline, will be presented. The n, minimum and maximum for observed percent change from baseline will be presented together as well.
- Descriptive summary including n, mean, SD, median, minimum, and maximum for absolute value, change from baseline and percent change from baseline at each visit will be presented. The visit includes baseline and Month 12 for liver volume and liver volume MN measured by MRI, and baseline, Month 3, 6, 9 and 12 for hemoglobin, platelet, chitotriosidase and Lyso-Gb1.

6.2.2. Sensitivity/Supplementary Analysis

There are no sensitivity and supplementary analyses planned for these endpoints.

6.3. Other Secondary Endpoints

- Estimand strategy: Treatment policy strategy for change from baseline in height SDS, weight SDS, tanner stage, bone age, BMD and Z-score for bone assessment, total score from mSST, as well as change from baseline in organ volume measured by ultrasound if available.
- Analysis set: FAS (defined in [Section 4](#)). All participants assigned to study drug and who take at least 1 complete dose of taliglucerase alfa (or partial dose if adverse events prevent completing infusion dose).
- Intercurrent events and missing data: Data after study drug discontinuation will be excluded; Missing values won't be included in calculating change from baseline and will not be imputed.
- Descriptive statistics including n, mean, SD, median, minimum, and maximum will be presented for observed continuous variables at each visit. This includes the absolute values, change from baseline and percent change from baseline in height SDS by chronologic age, height SDS by bone age, weight SDS by chronologic age, weight SDS by bone age, bone age, BMD and Z-score for bone assessment, right and left testis volume, total score from mSST, and spleen volume, spleen volume MN, liver volume, liver volume MN measured by ultrasound.

- BDM and Z-score for bone assessment will be descriptively summarized by each bone area, such as L femoral neck, total left hip, total body, etc. that listed in [Section 3.3.3](#).
- Frequency and percentage will be provided for categorical variables at each visit, such as tanner stage.

6.4. Other Endpoint(s)

6.4.1. Immunogenicity (Antibodies)

Frequency and percentage of anti-taliglucerase alfa antibodies in FAS will be reported at baseline, Month 6 and Month 12, if adequate data are collected.

